6.1.2 Randomisation procedure

If the patient is subsequently given a diagnosis of suspected bladder cancer and would still like to take part in the study, the patient will sign a second Informed Consent Form and will be randomised into the study.

Randomisation will be done online via the via the online electronic remote data capture system (eRDC) by logging on to: https://www.cancertrials.bham.ac.uk

An Eligibility Checklist must be completed and faxed to the Study Office before the online Randomisation Form is completed.

At the end of the randomisation procedure a report should be printed as a confirmation and filed in the Investigator Site File along with the original signed Informed Consent Form.

Emergency randomisation

If there are any problems with online randomisation, a paper eligibility checklist and randomisation form should be completed. These details should then be phoned through to the Study Office using the numbers below:

2 [name]; 9am-5pm Monday to Friday

Randomisation will be performed using minimisation on a 1:1 basis with the following stratification variables:

- Patient sex: male or female
- Age: <75 years old or ≥75 years old
- Clinician assessment: probable NMIBC or possible MIBC

The randomisation is not blinded, and therefore both participant and the health care team will know which pathway has been allocated to the participant.

7. STUDY PROCEDURE

The study is comparing TURBT with MRI for the assessment of possible MIBC. Patients will be randomised to either pathway 1 or 2 following their cystoscopy result and confirmation of suspicion of NMIBC or MIBC.

7.1 Standard Pathway 1

The current standard of care pathway comprises flexible cystoscopy in clinic combined with upper tract imaging and potentially cross sectional imaging of the bladder/pelvis. The establishment of such 'rapid access', 'urgent referral' or 'haematuria clinics' was first described in 1994^{35, 36}.

Patients with a bladder lesion then undergo rigid cystoscopy with tumour excision (TURBT under general anaesthesia). The exophytic component of the tumour is excised together with underlying detrusor muscle and both samples undergo definitive histopathological diagnosis. The clinical stage of the bladder tumour is also evaluated under anaesthesia.

7.1.1 TURBT

Transurethral resection of the bladder tumour should be conducted as recommended by the European Association of Urology (EAU) and British Association of Urological Surgeons (BAUS). In particular, resection of the exophytic component should be performed using a rigid resectoscope. Sampling of the underlying detrusor muscle is necessary, as is recording of the clinical stage following resection (complete, incomplete, semi-fixed, fixed mass etc.). Bladder neck or urethral sampling should be performed in patients suitable for neobladder reconstruction. Sampling of areas suspicious of carcinoma in situ (red areas or fluorescent with blue light) should be undertaken. A separate biopsy of the bladder tumour base should be taken. All samples should be sent for histopathological reporting and reviewed at a suitable clinical meeting.

7.2 Image-directed Pathway 2

Instead of TURBT, patients identified as possible MIBC patients will undergo mpMRI.

Criteria for diagnosing patients as possible MIBC are as follows:

- 1. Appearance on flexible cystoscopy
 - This includes the presence of a solid tumour in the bladder or a tumour seen infiltrating into the bladder wall or a solid tumour or mixed solid/papillary morphology.
 - This may also include the presence of a semi-fixed mass within the bladder found by examination before or after the flexible cystoscopy.
- 2. Cytological: The presence of high grade urothelial cells in either the urine cytology or in the flexible cystoscopy biopsy
- 3. If suitable, imaging obtained (e.g. CT Urography). This may also be used to identify possible MIBC.

The endoscopist carrying out the flexible cystoscopy will be asked to assess the likelihood that a bladder tumour is muscle invasive. If yes, and if either urine cytology or a biopsy taken at cystoscopy confirms the presence of high grade urothelial cancer cells then randomisation between pathways 1 and 2 is permitted.

Treatment proceeds via the standard pathway (without randomisation) for patients with either low grade histology or inconclusive visual appearances on cystoscopy.

7.2.1 mpMRI

Imaging will be carried out as per the Imaging Manual. The scans should be initially read at the local centre but secondary central reading by a certified radiologist will be performed for quality assurance and further research purposes.

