4.1 Inclusion criteria

- 1. Provision of written informed consent
- 2. Patients must be ≥18 years of age
- 3. Patients attending clinic for the investigation of symptoms suspicious of bladder cancer (initial consent process)
- 4. Patients given a diagnosis of suspected bladder cancer and requiring a TURBT based on visual cystoscopic examination of the bladder (confirmatory consent process, post cystoscopy)

Note: as the study does not involve additional drug therapy or ionising radiation, there are no restrictions on women of childbearing potential.

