13.2.1 Feasibility stage

To evaluate the feasibility of setting up Imaging-directed pathway 2 (e.g. assessing effects of increased MRI demand), this stage will evaluate 150 patients entered into the study – approximately 50 from each of the three pilot sites. This will allow for qualitative checks of feasibility to be made; such as willingness of patients to be randomised into the study.

Quantitatively, we will consider feasibility to have been demonstrated if we observe at least 80% of possible MIBC patients correctly follow pathway 2. That is, patients receive an MRI at the appropriate pathway stage. Of the 150 patients recruited for this stage, 75 patients will be randomised to pathway 2. We expect that around 50% of the pathway 2 patients will be diagnosed as *possible MIBC*; which results in a sample of around 38 patients scheduled to have a MRI. The power of observing feasibility is dependent on the true proportion of patients who correctly follow the pathway. The probability of observing that 80% of the sample correctly follows the protocol for a selection of suitable true proportions is given in Table 5, which provides good power to detect feasibility.

Table 5.Probability of a successful feasibility stage given 80% of possible MIBC
patients are observed to correctly follow the pathway

True proportion	Probability of observing feasibility
80%	66%
83%	81%
85%	90%
87%	95%
90%	99%

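### Section 7.2 withholds randomisation from patients whom section 6.1.2 randomises and section 13 counts on

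*Protocol*

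**What the plan says.** The protocol gives two rules for who is randomised.

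**Narrow rule (section 7.2).** The endoscopist judges whether the tumour is likely to be muscle invasive. If so, and if cytology or biopsy confirms high grade cells, "then randomisation between pathways 1 and 2 is permitted". The next sentence reads: "Treatment proceeds via the standard pathway (without randomisation) for patients with either low grade histology or inconclusive visual appearances on cystoscopy".

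**Broad rule (elsewhere).**
- Section 6.1.2: once bladder cancer is suspected and the patient still wishes to take part, "the patient will sign a second Informed Consent Form and will be randomised into the study". One of the minimisation factors is "Clinician assessment: probable NMIBC or possible MIBC".
- Section 7, opening: allocation to pathway 1 or 2 takes place "following their cystoscopy result and confirmation of suspicion of NMIBC or MIBC".
- Section 13.2.1: possible MIBC is expected in only about half of pathway 2, "which results in a sample of around 38 patients scheduled to have a MRI".
- Section 13.2.2: the 80-100 patients to be recruited follow from 20-25% MIBC among new bladder cancers.
- Table 2, section 13.3.3 (boxes A and C) and section 13.4 plan outcomes or subgroups for probable NMIBC patients.

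Section 4.1 is compatible with the broad rule. It admits "Patients given a diagnosis of suspected bladder cancer and requiring a TURBT based on visual cystoscopic examination of the bladder" and sets no condition on grade or invasion. The exclusions in 4.2 add none.

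**The concern.** A patient with a low grade papillary tumour who needs TURBT and has given second consent is randomised under 6.1.2 and treated outside the randomisation under 7.2. Both sentences are operative instructions to sites, and they cannot both be followed.

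The composition of the randomised population is at stake. It sets the denominator of the feasibility outcome and the recruitment needed for the intermediate stage. It also decides whether the probable NMIBC comparisons have any randomised patients. An analysis plan cannot repair this later, because sites enrol from the protocol.

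**Working it through.** **1. The two rules side by side**

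| Place | Suspected muscle invasion, high grade | Low grade or inconclusive |
|---|---|---|
| 7.2 | randomised | not randomised |
| 6.1.2 and opening of 7 | randomised | randomised |
| 13.2.1 | about half of pathway 2 | within the other half of pathway 2 |
| Table 2, 13.3.3, 13.4 | analysed as possible MIBC | analysed as probable NMIBC |

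Under 7.2 a patient can be randomised only if the endoscopist has already answered that invasion is likely. Almost nobody could then enter the minimisation as probable NMIBC.

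**2. Feasibility stage**

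Inputs: 150 patients and a 50% possible MIBC share (13.2.1), 1:1 allocation (6.1.2).
- Plan's figure: 150 / 2 = 75 in pathway 2; 75 × 0.50 = 37.5, stated as 38. This reproduces.
- Table 5 rests on the same 38. The exact binomial probability of at least 30 of 38 at true proportions of 80, 83, 85, 87 and 90% is 65.5, 81.4, 89.4, 94.9 and 98.9%. The stated values are 66, 81, 90, 95 and 99%.
- Under 7.2: all 75 pathway 2 patients would be possible MIBC and scheduled for MRI.
- 95% interval half-width at 80%, 1.96 × √(0.8 × 0.2 / n): 12.7 points at n = 38 and 9.1 points at n = 75.

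Precision would improve under 7.2, so the harm here is not statistical. The point is that 38 can arise only under the broad rule.

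**3. Intermediate stage**

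Inputs: 20 MIBC patients and 20-25% MIBC among new cases (13.2.2).
- Plan's figure: 20 / 0.25 = 80 and 20 / 0.20 = 100. This reproduces, and it uses the share among all new cases.
- Under 7.2, assuming that every MIBC lies within the 50% called possible MIBC, the MIBC share among randomised patients is 0.20 / 0.50 = 40% to 0.25 / 0.50 = 50%. Then 20 / 0.50 = 40 to 20 / 0.40 = 50 patients would suffice.

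**4. Final stage**

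Inputs: 380 events and a 40% overall recurrence rate (13.2.3).
- Plan's figure: 380 / 0.40 = 950. This reproduces.
- The 380 events follow from the hazard ratio of 0.75 and the power alone, so they do not tell the two rules apart.
- Under 7.2, randomising 950 would need 950 / 0.50 = 1,900 suspected cancers. If the possible MIBC share were 60% or 40% (assumed range), the need would be 950 / 0.60 = 1,583 or 950 / 0.40 = 2,375.

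**5. Limit of the 50% figure**

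Section 13.2.1 gives it for patients already in pathway 2. Steps 3 and 4 apply it to all suspected cancers. Section 7.2 also asks for high grade cells, so the share randomised under 7.2 could be below one half.

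**The case against.** The strongest reply is that the intent is not in doubt. The minimisation offers probable NMIBC as a level, 13.2.1 expects about half of pathway 2 to fall outside possible MIBC, and boxes A to D in 13.3 are defined by arm and initial assessment. The study schema figure was not available here and may show this plainly. Section 7.2 was probably meant to say who goes to mpMRI. All of this stands, and it is why 7.2 is called the outlier. It does not remove the fault: the sentence withholds randomisation, not MRI, and a site reading it literally would exclude patients whom the design needs.

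A reader might infer three stronger points, none of which the protocol supports.
- *That the final comparison is underpowered because about half of pathway 2 has TURBT in either arm.* That would be a question about the size of the effect under the broad rule, and correcting 7.2 would leave it untouched. Section 13.2.3 states the hazard ratio of 0.75 for pathway 2 as a whole. The protocol gives no separate effect for probable NMIBC and no split of events. Section 1.3 also expects faster treatment for NMIBC through lower demand for TURBT.
- *That sites have enrolled different populations.* The protocol shows only that they could.
- *That section 4.1 itself contradicts 7.2.* It lists eligibility, does not name NMIBC and randomises nobody. It merely sets no condition that would match 7.2.

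**Conclusion.** The contradiction is real and lies in the current operative text. Section 7.2 conflicts with 6.1.2, the opening of section 7, 13.2.1, 13.2.2 and the probable NMIBC analyses.

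If 7.2 were followed:
- the possible MIBC count in pathway 2 of the feasibility stage would be 75, not 38;
- the probable NMIBC minimisation level would be nearly or wholly empty;
- about half of suspected cancers would not be randomised, on the assumption that the 50% in 13.2.1 describes all suspected cancers.

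Under the broad rule the figures of 38, 80-100, 380 and 950 stand as far as this point is concerned. This is an instruction that is wrong as written and should be corrected. It is not a failure of the sample size.

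A small related slip: 13.3.3 attaches the stratification label to tumour grade, although the factor in 6.1.2 is the clinician assessment, which the same sentence of 13.3.3 enters separately. Correcting the label changes no result.

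**What to change.** Reword the two randomisation sentences in 7.2 so that they assign mpMRI within pathway 2. For example:

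> If yes, and if high grade cells are confirmed, the patient is classed as possible MIBC and, if allocated to pathway 2, undergoes mpMRI. Patients not classed as possible MIBC are also randomised and proceed to TURBT in either pathway.

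Leave the listed criteria for possible MIBC unchanged, including the one that allows imaging to be used. In 13.3.3, move the stratification label to the initial cystoscopic assessment.

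The cost is two sentences, one label and a note to sites. There are no new data items and no change in care for low grade or inconclusive patients, who have TURBT in either pathway. The dependence on a cytology or biopsy result is already in 7.2 and is neither added nor removed.

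If the sponsor does intend the narrow rule, the changes belong elsewhere and are larger: 4.1, 6.1.2, the opening of section 7, the figures in 13.2.1 and 13.2.2, and every probable NMIBC analysis.

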7.3 Assessments

Initial clinic (visit 1)

- Medical history
- FBC
- Liver function test (LFT)
- Urea & electrolytes (U+E)
- Collection of urine and blood samples for translational research
- Concomitant medication
- Completion of EORTC-QLQ-BLM30 and EORTC-QCQ-30 (Quality of life questionnaires)
- Completion of EQ-5D-5L questionnaire (health economics)

Study procedure (visit 2)

• Review of adverse events

Decision to treat (visit 3)

- Medical history
- FBC
- Liver function test (LFT)
- Urea & electrolytes (U+E)
- Collection of urine and blood samples for translational research
- Review of adverse events

Follow-up (3, 6, 9, 12, 18, 24 months and annually to 5 years)

- Collection of urine and blood samples for translational research (only once at any point after treatment during a routine visit)
- Completion of EORTC-QLQ-BLM30 and EORTC-QCQ-30 (Quality of life questionnaires)
- Completion of EQ-5D-5L questionnaire (health economics)

7.4 Sample Collection

Table 3 summarises the samples that are to be taken during the study.

Table 3. Samples to be taken

Sample	Routine	Biomarker sub-study
Blood	10 ml	10 ml + 3.5 ml (additional)
Urine	200 ml	50 ml (taken from the routine sample)
Tumour biopsy	Biopsy sufficient to confirm malignancy	Biopsy sufficient for DNA extraction. Minimum 0.2 mm

*Collection of urine and blood samples (visits 3 & 4) would be subject to securing funding.

7.5 Treatment recommendations

Please refer to National Institute for Health and Care Excellence (NICE) guidelines for bladder cancer treatment and management³². Other relevant guidelines such as the European Association of Urology (EAU) guidelines¹⁵ or other local guidelines may also be followed.

7.6 Compliance

All analyses will be by intention to treat. The initial feasibility stage will assess compliance with the protocol and feasibility of implementation.

7.7 Concomitant illness and medication

The intervention is an imaging-directed pathway for diagnosis and staging. Patients will inevitably have concomitant illnesses that will affect compliance with both treatment pathways. Concomitant illness and medication will be recorded at study entry and follow-up visits. Aside from contraindications to mpMRI, there are no medication- or illness-related exclusions. This will ensure the broadest possible applicability of findings from the study.

7.8 Patient follow-up

Patients will be followed-up every 3 months until 12 months, every 6 months until 24 months and annually from 24 months to 5 years from the date of randomisation.

7.9 Patient Withdrawal

Participants may discontinue from the study at any time without prejudice. Unless a participant explicitly withdraws their consent, they should be followed-up wherever possible and data collected as per the protocol until the end of the study. Bio-specimens (urine, blood and tumour samples) obtained prior to study discontinuation will continue to be utilised (anonymously) for translational research unless such consent is explicitly withdrawn.

Participants may be withdrawn from the study at the discretion of the investigator and/or Trial Steering Committee due to safety concerns or due to any condition which in the opinion of a local investigator might interfere with the safety of the patient or the evaluation of the study objectives.

8. ADVERSE EVENT REPORTING

The collection and reporting of Adverse Events (AEs) will be in accordance with the Research Governance Framework for Health and Social Care and the requirements of the National Research Ethics Service (NRES). Definitions of different types of AE are listed in Appendix 2. The Investigator should assess the seriousness and causality (relatedness) of all AEs experienced by the patient (this should be documented in the source data) with reference to the protocol.

8.1 Reporting Requirements

8.1.1 Adverse Events

MRI and TURBT are both well documented and widely used procedures. As the safety profiles of both procedures are well characterised, only Serious Adverse Events (SAEs) experienced due to the procedures will be reported.

8.1.2 Serious Adverse Advents

Investigators should report AEs that meet the definition of an SAE (see Appendix 2 for definition) and are not excluded from the reporting process as described below.

8.1.2.1 Expected Serious Adverse Events

We are not expecting any SAEs to occur as a result of participation in this study.

Expected serious adverse events do not need to be reported to the study team.

The following are regarded as expected SAEs for the purpose of study and should not be reported on an SAE form:

- BladderPath
 - Anaemia
 - Bladder discomfort/pain
 - Bladder perforation
 - Bleeding resulting in clot retention
 - Constipation
 - Contrast reaction
 - Diarrhoea
 - Deep Vein Thrombosis (DVT)
 - Fever
 - Gout
 - Haematuria
 - SAEs that are thought to have occurred as a result of the patient's cancer treatment
 - SAEs that are related to symptoms or progression of the patient's cancer

- Insomnia
- Nausea
- Postoperative dysuria
- Prolonged catheterisation
- Skin rash
- Urethral stricture
- Urinary frequency
- Urinary retention
- Urinary tract infection
- Vomiting
- Increased white blood cell count
- SAEs that are related to a pre-existing condition
- Death from cancer, as a result of the patient's cancer treatment or from a preexisting medical condition

This is not an exclusive list and Investigators should only report SAEs which are attributable to the study protocol.

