Appendix	x 1 - World Medical Association Declaration of Helsinki	39	
	Appendix 2 - Definition of Adverse Events 42		
Appendix	x 3 - Common Toxicity Criteria Gradings	42	

BACKGROUND AND RATIONALE 1.

Background 1.1

Bladder cancer is the fifth most common cancer in western society, with a rising global incidence and 430,000 new cases in 2012^{1,2}. In the UK there are approximately 10,000 new cases and 5,000 deaths attributed to bladder cancer annually³. In western populations, over 90% of bladder cancers are urothelial cell carcinoma (UCC). Standard management follows a pattern established during the 1950s with the development of the rigid cystoscope. Prognosis has not improved in the last 30 years³⁻⁵.

Standard management involves a pathway of diagnostic flexible cystoscopy followed by a transurethral resection of the bladder tumour (TURBT) with a rigid cystoscope. TURBT has the multiple purposes of diagnosis, staging and treatment of non-muscle invasive bladder cancer (NMIBC), i.e. removal of the tumour. Further treatment such as radical cystectomy or chemoradiotherapy is then necessary for muscle invasive bladder cancer (MIBC).

For MIBC, this initial TURBT often understages invasion (up to 30% of MIBCs are initially staged as high grade NMIBC at first TURBT)⁶, and may contribute to extra-vesical tumour dissemination through bladder perforation or venous emboli generated through the high-pressure resection process⁷. Crosssectional pelvic imaging after TURBT impedes the accuracy of staging due to surgical artefacts (such as perivesical inflammation and reactive lymph nodes)⁸⁻¹¹.

Typically, the need for a TURBT, histopathological review and MDT decision-making adds at least 6-12 weeks to the pathway, prolonging the delay to commencing (the most appropriate) definitive radical treatment for patients with MIBC^{6, 12-14}.

An ideal pathway would separate NMIBC patients from MIBC patients at the time of diagnosis. Faster and more accurate application of established technologies would streamline therapy, potentially improve outcomes and save clinical costs.

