2.2 Outcome Measures

The primary and secondary outcomes change as we go through the study. These are summarised in Table 2.

	Primary Outcomes	Secondary Outcomes
Feasibility stage	The proportion of possible MIBC patients randomised to pathway 2 who correctly follow pathway protocol	 Overall proportion of patients who correctly follow protocol Recruitment and retention rates at each study site Counts of each definitive treatment
Intermediate stage	The time to definitive treatment (TTDT) for all possible MIBC patients	 TTDT for all patients TTDT for probable NMIBC patients Proportion of all patients who correctly follow pathway protocol Recruitment and retention rates at each study site
Final clinical stage	Clinical progression-free survival (CPFS)	 Cost effectiveness of each pathway Patient Quality of life The proportion of patients who correctly follow pathway protocol

Table 2.Primary and Secondary Outcomes

1 1	TTDT for all a socible MIDO a stights
	TTDT for all possible MIBC patients
	 TTDT for all probable NMIBC patients
	TTDT for all MIBC patients
	TTDT for all NMIBC patients
	Time to correct treatment
	Time to each treatment type
	Time to recurrence, progression or metastatic disease progression
	Number of recurrences; progressions and incidence of metastatic disease
	Number of each type of treatment(s) received
	 Accuracy of MRI/TURBT by comparison with histological confirmed diagnoses
	Overall and disease specific survival
	Number of unnecessary radical cystectomies
	Number of SAEs

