8.2.5 Data Monitoring Committee

The independent Data Monitoring Committee (DMC) will review all SAEs.

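### Listed serious harms of TURBT and MRI are kept out of SAE reporting altogether, so the SAE-count outcome and the SAE reports to the DMC cannot show a difference between pathways in those harms

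*Protocol*

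**What the plan says.** Section 8.1.1 limits safety reporting: "only Serious Adverse Events (SAEs) experienced due to the procedures will be reported". Section 8.1.2 then asks for SAEs that are not excluded by the text that follows it. Section 8.1.2.1 opens with "We are not expecting any SAEs to occur as a result of participation in this study", continues with "Expected serious adverse events do not need to be reported to the study team", and introduces its list with "The following are regarded as expected SAEs for the purpose of study and should not be reported on an SAE form". The list has 22 named events and four classes: SAEs from cancer treatment, from cancer symptoms or progression, from a pre-existing condition, and deaths from any of these causes. "Bladder perforation" is one of the named events and contrast reaction is another. The section adds that the list is not exhaustive and that only SAEs attributable to the protocol should be reported. The site procedure in section 8.2.1.1 repeats the exclusion.

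Two other parts of the protocol rely on SAE data. Table 2 in section 2.2 makes "Number of SAEs" a secondary outcome of the final clinical stage. Section 8.2.5 says that the DMC "will review all SAEs". Section 1.1, giving the reasons for the trial, says that TURBT "may contribute to extra-vesical tumour dissemination through bladder perforation".

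**The concern.** It is normal to exempt well-known complications from expedited reporting. Here sites are told not to send the events to the study team at all, and no other stated route carries them to the outcome or to the DMC. The experimental pathway replaces TURBT with MRI in possible MIBC, so the complications of those two procedures are the safety contrast of most interest, and they are what the list removes. One of them, perforation, is part of the trial's own rationale.

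The loss is probably unequal between arms, since most of the listed procedural harms are surgical. Section 8.2 also calls MRI the only study intervention, so an investigator may judge even an unlisted TURBT complication not attributable to the protocol. The reported SAE count could then hide a real safety advantage of avoiding TURBT. In the other direction, serious contrast reactions to the study MRI would not reach the DMC through SAE reports.

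**Working it through.** The protocol gives no SAE rate, safety sample size or safety power, so there is no planned figure to reproduce. The check is to follow a listed event through the reporting chain and then to put a rough size on what is lost.

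**Reporting chain for a serious bladder perforation after TURBT**

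1. Appendix 2: it qualifies as an SAE if, for example, it causes an unplanned admission.
2. Sections 8.1.2 and 8.1.2.1: it is on the list, so it is not reported to the study team and does not go on an SAE form.
3. Section 8.2.1.1: the site procedure excludes it again.
4. Section 8.2.2: the Clinical Coordinator assesses related SAEs for expectedness, but this one never arrives.
5. Section 8.2.5: the DMC is to review all SAEs, but has no SAE report of it.
6. Section 2.2, Table 2: it adds 0 to the SAE count, in either arm and whatever its true rate.

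A serious contrast reaction after MRI follows the same path. An unlisted SAE that the investigator attributes to the protocol passes every step and is counted.

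**Other possible routes**

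- Section 7.3 has a review of adverse events at visits 2 and 3, but Table 4 and the ad hoc forms in section 10.1 include no adverse event form other than the SAE form.
- The TURBT and MRI Forms record details of the procedure. Complications are not mentioned.
- HES data (sections 10.1 and 14) cover inpatient stays, and the cost-consequence analysis in section 14 mentions side-effects. Neither is linked to the SAE outcome or to the DMC.
- Deaths are on the Death Form and progression is on the Recurrence Form, so those exempt classes lose little.

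**Rough size**

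Inputs:
- 950 patients (section 13.2), randomised 1:1 (section 6.1.2).
- About 50% possible MIBC (section 13.2.1, stated for pathway 2). Minimisation on the clinician's assessment makes the same share reasonable in pathway 1.
- Serious TURBT complication rate of 2-10%. This is an assumption; the protocol gives no rate.

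Calculation:
- Patients per arm: 950 / 2 = 475.
- Possible MIBC per arm: 475 x 0.5 = 237.5, about 238.
- Hidden difference at 2%: 237.5 x 0.02 = 4.75, about 5 events.
- Hidden difference at 10%: 237.5 x 0.10 = 23.75, about 24 events.

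This treats every possible MIBC patient in pathway 1 as having TURBT and none in pathway 2. Some in pathway 2 will still have one, because MRI may show non-muscle-invasive disease or symptoms may need palliation (section 1.2). For the TURBT harms, 5-24 is therefore towards the upper end at each assumed rate.

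**The case against.** **The sections can be read together.** Section 8.1.2 links 8.1.1 to the exclusions, and 8.2.1.1 repeats them, so a site knows what to do. This largely stands. A reader might infer a flat contradiction between 8.1.1 and 8.1.2.1, but the text does not support that. The statement that no SAEs are expected, placed above a list of expected SAEs, is poor wording with little practical effect. The real mismatch is between the reporting rule and its two users, the outcome in section 2.2 and the DMC review in section 8.2.5.

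**The SAE count still carries information.** A reader might infer that it will be near zero in both arms, or that the pathways' safety cannot be compared at all. The protocol supports neither, since unlisted attributable SAEs are still reported.

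**The size can be overstated.** Applying 2-10% to all of pathway 1 gives 475 x 0.02 = 9.5 to 475 x 0.10 = 47.5, about 10-48 events. That is the number uncounted in one arm, not a difference between arms. Probable NMIBC patients have TURBT in both arms under the same rule.

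**Events may be captured elsewhere.** Procedure forms, visit reviews, HES and the Death Form may hold some of them, and the form contents and SAE completion guidelines are not shown. Section 15.5 also gives the DMC data analyses and allows emergency safety meetings. It is therefore not established that these events are lost to the trial. But nothing in the protocol sends them to the SAE outcome or to the DMC, and that gap remains.

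**Both procedures are well characterised.** Section 8.1.1 gives this as its reason. It justifies not expediting known complications. It does not justify leaving them out of a comparison between a pathway with TURBT and one that aims to avoid it.

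**Conclusion.** The point holds for the listed harms. By rule they contribute nothing to the SAE-count outcome and do not reach the DMC through SAE reports, so that outcome cannot show a difference between pathways in perforation, clot retention, thrombosis, urinary infection or contrast reaction. This conclusion rests on the text alone and needs no event rate.

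The size, roughly 5-24 hidden events of between-arm difference, rests on the assumed 2-10% rate and on the 50% possible MIBC share in section 13.2.1.

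This should be fixed, but it is not critical. It concerns one of many final-stage secondary outcomes and the safety information for the DMC. No primary outcome, sample size or primary analysis changes. An analysis plan could not repair it, because an SAE count cannot include events that sites are told not to submit.

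**What to change.** Keep the listed events classed as expected and exempt from the 24-hour SAE form and from ethics committee reporting. In addition:

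1. Require every listed event that meets the Appendix 2 seriousness definition to be recorded on the existing TURBT, MRI or Follow-up eCRF, in the same way in both arms.
2. State in section 2.2 that these events count by arm in the SAE outcome.
3. Tabulate them by arm for the DMC.
4. Align the wording of sections 2.2, 8.1.1, 8.1.2.1, 8.2.1.1 and 8.2.5 with this.

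Bladder perforation and contrast reaction should not simply be taken off the expected list. Section 8.2.1.1 would then require a report within 24 hours. Under sections 8.2.2 and 8.2.3.1, a related case would be classed as unexpected and go to the ethics committee within 15 days, although both are known complications.

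The cost is slightly more data entry at sites and one extra DMC table. Section 10.1 allows forms to change without a protocol amendment, but the protocol wording itself needs correcting.
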